#### **PPC**

The subjects presenting with at least one of the following relevant protocol deviations will be excluded from the PPC:

- Subject did not meet all protocol-specified inclusion criteria or met at least one of the protocol-specified exclusion criteria
- Subjects identified as dengue non-immune subjects (seronegative) at baseline
- Subject did not complete the vaccination schedule
- Subject received a vaccine other than the one that she was randomized to receive
- Administration of vaccines was not done as per-protocol (site and route of administration)
- Subject did not receive vaccines in the proper time window
- Subject did not provide after the 3rd dose of CYD dengue vaccine a post-dose serology sample in the proper time window or a post-dose serology sample was not drawn (V08, M13 for Group 1 and M14 for Group 2)
- Subject received a protocol-prohibited medication (prohibited therapies/medications/vaccines are indicated in Section 6.7) (until V07)
- Subject's serology sample did not produce a valid test result, ie, no Neutralizing Ab titers against any of the four parental dengue virus serotypes of CYD dengue vaccine available (at V08, M13 for Group 1 and M14 for Group 2)

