- **Subjects identified as dengue exposed, choosing to receive the last CYD dengue vaccine injection.** The procedures described for Visit 4 will be followed, except that no dose of Cervarix will be injected and CYD dengue vaccine will be injected to all eligible subjects (third and last dose, given 12 months post-injection 1, depending on the duration of the study pause).
- **Subjects identified as dengue exposed, choosing not to receive the last CYD dengue vaccine injection AND subjects identified as dengue unexposed:**
 - a) Give the parent(s)/legally acceptable representative(s) a memory aid (MA).
 - b) Remind the parent(s)/legally acceptable representative(s) to keep the MA available when they will be called for Safety Follow-up Telephone Call at a specified date and time.
 - c) Complete the relevant CRF pages for this visit.
 - d) Complete the termination record of the CRF.

The following visit procedures will only apply to Subjects identified as dengue exposed, choosing to receive the last CYD dengue vaccine injection

Phone Call 7 (PC5) (7 days [+8 days] after Visit 7)

The same procedures as those described for PC1 will be followed.

Visit 8 (Month 13 (Group 1) or Month 14 (Group 2); 28 [+14] days after Visit 7)

The Investigator or designated study personnel will:

- 1) Review the pages of the DC with the parent(s)/legally acceptable representative(s), including any AEs, medications, or therapy that occurred since vaccination.
- 2) Perform a physical examination and record the subject's axillary temperature.
- 3) Check concomitant medications and record every reportable medication ongoing at the time of vaccination.
- 4) Obtain a blood sample (see [Section 7.1](#) for detailed instructions regarding the handling of blood samples).
- 5) Give the parent(s)/legally acceptable representative(s) a memory aid (MA).
- 6) Remind the parent(s)/legally acceptable representative(s) to keep the MA available when they will be called for Safety Follow-up Telephone Call at a specified date and time.
- 7) Complete the relevant CRF pages for this visit.
- 8) Complete the termination record of the CRF.

Phone Call 8 (PC8) (approximately 2 months after Visit 8)

The same procedures as those described for PC1 will be followed.

Safety Follow-up (6-month period after last vaccination) for all subjects, exposed and unexposed, having accepted to continue participation in the trial post-amendment 1

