6.7 Concomitant Medications and Other Therapies

At the time of enrollment, ongoing medications including other therapies e.g., blood products, should be recorded in the source document as well as new medications prescribed for new medical conditions/AEs during trial participation.

Documentation in the CRF of concomitant medication will be limited to specific categories of medication of interest beginning on the day of vaccination. This may include medications of interest that were started prior to the day of vaccination.

Reportable medications will be collected in the CRF from the day of vaccination to the end of the solicited and unsolicited follow-up period (e.g., 28 days safety follow-up) as they may impact the response to the vaccination and impact the consistency of the information collected on concomitant medications at any vaccination.

The “reportable” medications are distributed according to two categories. These are:

- Category 1 (Restricted therapies): antipyretics, analgesics, non steroidal anti-inflammatory drugs (NSAIDs), corticosteroids, and other immune modulators.

Note: inhaled and topical steroids should not be captured.

- Category 2 (Prohibited therapies for the PP):

- Immunosuppressive therapy such as anti-cancer chemotherapy or radiation therapy or long-term systemic corticosteroids (for more than 2 consecutive weeks) in the 4 weeks after each trial vaccination
- Immune globulins, blood or blood-derived products in the 4 weeks before and after each trial vaccination
- Vaccines (other than the trial vaccines) in the 4 weeks before and after each trial vaccination

The information reported in the CRF for each reported medication will be limited to:

- Trade name
- Given as treatment or as prophylaxis
- Medication category
- Start and stop dates

Dosage and administration route will not be recorded. Homeopathic medication will not be recorded. Topical treatment will not be recorded.

The fact that a medication was given in response to an AE will be captured in the “Action Taken” column of the AE only. No details will be recorded in the concomitant medication module of the CRF unless the medication received belongs to one of the prelisted categories. Medications will not be coded.

7 Management of Samples

Blood samples for the assessment of antibody responses will be collected at Visits 1, 2, 3, 5, 6, and 8. See the [Table of Study Procedures](#) and [Section 5.1.4](#) for details of the sampling schedule.

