Virological confirmation of dengue***	All acute febrile illness with diagnosis of dengue requiring hospitalization within the first 5 days after fever onset, occurring anytime throughout the trial period								
Vaccine injection	Cervarix Dose 1 (Groups 1 and 2)  CYD Dose 1 (Group 1)	CYD Dose 1 (Group 2)		Cervarix Dose 2 (Groups 1 and 2)  CYD Dose 2 (Group 1)	CYD Dose 2 (Group 2)		CYD Dose 3 (Groups 1 and 2)		
Post-injection phone call†††	Interim phone calls will be given 7 days after each injection and 2 months after blood samples during the 6-month period after each vaccination.								
Diary Card (DC)									
Provided	X	X (Group 1 for SAE only and Group 2)  X X	X (Group 2 for SAE only)	X	X (Group 1 for SAE only and Group 2)  X X	X (Group 2 for SAE only)	X		
Checked Collected						X (Group 2) X (Group 2)	X X	X X	
Memory Aid (MA)						X	X	X	X
Provided### Checked									
30-Min. Observation Period	X	X (Group 2)		X	X (Group 2)		X		
Injection Site Reactions & Systemic Events Assessment\$\$\$\$	X	X	X (Group 2)	X	X	X (Group 2)	X	X	
Collection of SAEs, and serious AESIs\$\$\$\$	Throughout the trial period (for SAEs) or in defined time windows according to the type of AESI								
Termination Record****							X		

Abs: antibodies; AE: Adverse event; AESI: AE of special interest; BL: blood sample; CYD: CYD dengue vaccine; D: Day; M: Month; SAE: Serious adverse event; V: Visit;

---

- \* Visits to be performed by dengue immune subjects only, if they consent to receive the next CYD vaccine injection
- † Vaccinations and associated or subsequent procedures may be out of the defined time-windows in dengue-immune subjects continuing the study due to study pause
- ‡ All subjects will either attend an unscheduled visit (V00) or have an unscheduled phone call (PC00) during the study pause and **before** the next scheduled visit (V07 for most subjects; V08 for 2 subjects). During the unscheduled visit or phone call, the subject will be informed about the new safety data thanks to a “dear participant letter” and on their baseline serostatus result. The signature of the ICF/AF by the parents/subjects and the check of contraindications to continue in the study will be performed at the next visit planned, as applicable.
- § The 6-month phone call will be given to all subjects who consented to continue in the study whether they were identified as “dengue-immune” or “dengue non-immune”

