### ***Non-inferiority on CYD Dengue Vaccine***

The objective is to demonstrate that the humoral immune response to the CYD dengue vaccine administered concomitantly with Cervarix is non-inferior to the immune response to CYD dengue vaccine administered sequentially with Cervarix.

Individual hypotheses on CYD response for each antigen:

A non-inferiority testing approach will be used to compare GMTs 28 days after the third injection of CYD dengue vaccine between groups for each serotype “i” based on the following individual hypotheses:

$$H_0^i: \text{GMT}_{\text{Group1}}^i / \text{GMT}_{\text{Group2}}^i \leq \frac{1}{\delta} \Leftrightarrow \log_{10}(\text{GMT}_{\text{Group1}}^i) - \log_{10}(\text{GMT}_{\text{Group2}}^i) \leq -\log_{10}(\delta)$$

$$H_1^i: \frac{1}{\delta} < \text{GMT}_{\text{Group1}}^i / \text{GMT}_{\text{Group2}}^i > \frac{1}{\delta} \Leftrightarrow \log_{10}(\text{GMT}_{\text{Group1}}^i) - \log_{10}(\text{GMT}_{\text{Group2}}^i) > -\log_{10}(\delta)$$

with:

i, serotypes in {1, 2, 3, 4}

$\delta$  non-inferiority limit is set at 2 ie, 0.301 ( $=\log_{10}[2]$ ), for each serotype “i”

Non-inferiority for serotype i will be demonstrated if the lower bound of the 2-sided 95% CI is greater than  $-\delta$ .

Global hypotheses for non-inferiority on CYD response

$H_0^G: \text{at least one } H_0^i \text{ not rejected}$

$H_1^G: \text{all } H_0^i \text{ are rejected}$

Overall, non-inferiority among the groups will be demonstrated if, for each antigen of Cervarix and each serotype of CYD dengue vaccine, the 2-sided 95% CIs lie above  $-\delta$ .

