#### **PPX**

The subjects presenting with at least one of the following relevant protocol deviations will be excluded from the PPX:

- Subject did not meet all protocol-specified inclusion criteria or met at least one of the protocol-specified exclusion criteria
- Subjects identified as dengue non-immune subjects (seronegative) at baseline
- Subject is seropositive at baseline for Cervarix (ie, at least one Ab levels against Cervarix HPV antigens > LLOQ at baseline)
- Subject did not complete the Cervarix vaccination schedule (until V05 for Group 1, V06 for Group 2)
- Subject received a vaccine other than the one that she was randomized to receive (until V05 for Group 1, V06 for Group 2)
- Administration of vaccine was not done as per-protocol (site and route of administration)

- Subject did not receive vaccine in the proper time window (until V05 for Group 1, V06 for Group 2)
- Subject did not provide after the 2nd dose of Cervarix a post-dose serology sample in the proper time window or a post-dose serology sample was not drawn (V05 for Group 1, V06 for Group 2)
- Subject received a protocol-prohibited medication (prohibited therapies/medications/vaccines are indicated in the Protocol Section 6.7) (until V05 for Group 1, V06 for Group 2)
- Subject's serology sample did not produce a valid test result, ie, no Cervarix antigen titer available

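### The PPC prohibited-medication exclusion ends at the dose 3 visit (V07), although Protocol 6.7 prohibits these therapies for 4 weeks after dose 3

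*SAP*

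**What the plan says.** - **PPC rule.** SAP 5.2.2 (PPC) removes subjects who received prohibited products, which "are indicated in Section 6.7) (until V07". Protocol 12.2.2 uses the same cut-off.
- **What V07 is.** SAP Table 3.1 places "CYD Dose 3 (Groups 1 and 2" at V07.
- **Endpoint.** SAP 5.1.1.1 will "compare GMTs 28 days after the third injection of CYD dengue vaccine between groups". That sample is V08, which Protocol 5.1.4 schedules "28 [+14] days after Visit 7". A PPC subject must have it: the SAP excludes anyone for whom "Subject did not provide after the 3rd dose of CYD dengue vaccine a post-dose serology sample in the proper time window", or for whom it was not drawn.
- **What is prohibited, and when.** Protocol 6.7 (Category 2, prohibited for the per-protocol analysis) gives three windows tied to each trial vaccination. Immunosuppressive therapy is listed up to "long-term systemic corticosteroids (for more than 2 consecutive weeks) in the 4 weeks after each trial vaccination". Immune globulins and blood products are barred for 4 weeks before and after. The third item is "Vaccines (other than the trial vaccines) in the 4 weeks before and after each trial vaccination".
- **Parallel rule for Cervarix.** For the PPX, the SAP says that prohibited products "are indicated in the Protocol Section 6.7) (until V05 for Group 1, V06 for Group 2".
- **Data.** The footnotes to SAP Table 3.1 and to the Protocol's Table of Study Procedures say that concomitant therapy is collected for Days 0 to 28 after each injection.

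**The concern.** Protocol 6.7 says which exposures disqualify a subject from the per-protocol analysis, and its windows extend 4 weeks past every dose. The PPC criterion cites that section and then ends at the last dose. The two do not fit together for dose 3, the dose whose response is the primary dengue endpoint.

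At stake is who belongs to the set on which the CYD non-inferiority test is run. SAP 5.2.5 names only the PPC for that test. The confirmation on exposed subjects of the full analysis set, planned in Protocol 12.2.5, no longer appears there, so the PPC definition carries the result. PPC membership also feeds the count of evaluable subjects that decides whether non-inferiority is tested at all (163 per group for the co-primary objectives, SAP 5.5). Two programmers could build two different sets from the present wording.

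**Working it through.** **1. Line up the dates around dose 3 (V07 = day 0).**

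| Interval | Protocol 6.7 | PPC criterion, read literally |
|---|---|---|
| 4 weeks before V07 | Immune globulins/blood products and other vaccines prohibited | Screened |
| Days 0–28 after the V07 injection | All three classes prohibited | Not screened |
| Days 29–42 (only if V08 is late in its +14-day window) | Not prohibited | Not applicable |

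The gap is therefore 28 days. For immunosuppressants, Section 6.7 has only a post-vaccination window, so on the literal reading the criterion does nothing at dose 3 for that class.

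**2. Does another PPC criterion close the gap?**
- Receipt of a vaccine other than the randomized one carries no visit limit. It reads as a wrong study vaccine; at most it reaches non-trial vaccines, not the other two classes.
- Exclusion criterion 3 (Protocol 5.2.5) concerns vaccines already planned at enrolment.
- The definitive contraindications (Protocol 5.2.7.2) stop later doses. After dose 3 none remains.
- The rest concern serostatus, dosing, and sample timing and validity.

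Nothing covers a new immunosuppressant or immune globulin after dose 3.

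**3. Possible effect on the comparison.** The documents give no exposure rate or effect on titer, so both are assumed: a share f of 1% to 5%, and a drop d of 0.301 to 1.0 log10.
- *One group only:* shift in its mean = f × d. Smallest: 0.01 × 0.301 = 0.003. Largest: 0.05 × 1.0 = 0.05. The margin is 0.301.
- *Both groups, with exposed subjects pulled to a common low level:* a true difference Δ is seen as (1 − f)Δ. With Δ = 0.301 and f = 0.05 this is 0.286, a loss of 0.015.
- *Variance alone:* the SD becomes √(SD² + f(1 − f)d²). For serotype 1 (SD 0.9), f = 0.05 and d = 1.0: √(0.81 + 0.0475) = 0.926. With 163 per group the CI half-width, 1.96 × SD × √(2/163), goes from 0.195 to 0.201. The interval widens, which makes non-inferiority harder to show.

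**4. Cost of the fix in power.** Inputs from SAP 5.5: margin 0.301, one-sided alpha 0.025, SDs 0.4, 0.4, 0.9, 0.7, 0.7 and 0.5, true difference 0. Global power is the product of the six powers. The plan states 90.2% (204 per group) and 80.3% (163 per group). The noncentral t gives 0.9045 and 0.8058, and the normal approximation 0.9061 and 0.8090, so the plan's figures are reproduced to within one point.

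Now assume the fix removes 1%, 2% or 5% of the PPC (n rounded down; noncentral t). The starting value of 170 is an assumed middle case.

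| Starting n per group | 1% removed | 2% removed | 5% removed |
|---|---|---|---|
| 204 | 201: 89.9% | 199: 89.6% | 193: 88.4% |
| 170 | 168: 82.2% | 166: 81.6% | 161: 79.9% |
| 163 | 161: 79.9% | 159: 79.2% | 154: 77.4% |

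**The case against.** **The wording can be read another way.** Section 6.7 ties its windows to vaccinations, and V07 is the last one. The cut-off could mean the windows of all vaccinations up to and including V07, which would cover the 28 days. This reading is possible, and it is why the finding is stated as literal wording that is at best ambiguous. The PPX wording speaks against it: V05 in Group 1 and V06 in Group 2 are not injection visits for those groups. They come 28 days after the preceding injection, so there the label marks where checking ends.

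**The PPX is not a clean model.** A reader might infer that the PPX always screens through its endpoint sample and that the PPC breaks that rule. This holds only for Group 1. Protocol 9.1.1.2 assays HPV antibodies at V01, V02 and V05, so V06 in Group 2 is not an HPV sampling visit. The case rests on the conflict with Section 6.7, not on symmetry with the PPX.

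**The gap is not the whole interval to V08.** A reader might count all 28 to 42 days. Days 29 to 42 are neither prohibited by Section 6.7 nor within the scheduled collection of concomitant therapy.

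**Direction of bias.** A reader might say that contamination favours non-inferiority. Extra variance does the opposite. An equal drop at equal frequency in both groups cancels. Only a pull toward a common level dilutes a true difference. Both groups receive CYD alone at V07, so the documents give no reason to expect unequal exposure; a drop confined to Group 1 would count against non-inferiority.

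**Small numbers.** Subjects are enrolled healthy, planned vaccines are excluded at entry, and immunosuppression before dose 3 stops dosing. These narrow the gap but do not close it.

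**Conclusion.** The point stands in limited form. As written, the PPC criterion conflicts with Protocol 6.7 over the 28 days after dose 3, and no other criterion repairs this for immunosuppressants or for immune globulins and blood products. It is a defect inside the plan, not a disagreement between Protocol and SAP, since both carry the same cut-off.

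The expected effect on the result is small. Under the assumed 1% to 5% exposure and 0.301 to 1.0 log10 drop, one group's mean moves by at most 0.05, and dilution of a difference as large as the margin is about 0.015. The documents do not support a claim that the conclusion would change, or that the rule tilts the test toward non-inferiority. The reason to act is that membership of a primary analysis set should be unambiguous before counts and titers are examined.

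**What to change.** In Protocol 12.2.2 and SAP 5.2.2 (PPC), replace the V07 cut-off of the prohibited-medication criterion with: *until V08, applying the Section 6.7 windows, i.e. including the 4 weeks after dose 3*. In the SAP, cite *Protocol Section 6.7*, as the PPX criterion does; the SAP has no Section 6.7 of its own.

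No new data are needed, because concomitant therapy is already collected for Days 0 to 28 after each injection. The change restores the 4-week window and adds nothing for days 29 to 42. Its only downside is possibly a few fewer PPC subjects. From 204 per group, a loss of up to 5% leaves global power at about 88% or more. The loss matters only if the count lies close to 163 per group, where it could turn the planned test into a descriptive analysis. The wording should therefore be settled before the evaluable subjects are counted.

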#### **5.2.3 Safety Analysis Set**

The SafAS is defined as those subjects who have received at least one dose of the study vaccines. All subjects will have their safety analyzed after each dose according to the vaccine they actually received, and after any dose according to the vaccine received at first dose. The safety data will also be presented separately for dengue immune, non-immune / undetermined subjects.

Safety data recorded for a vaccine received out of the protocol design will be excluded from the analysis (and listed separately).

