Dengue unexposed subjects will not receive further dengue vaccine injection. If they consent to continue their participation in the study, they will be contacted by phone call for a safety follow-up 6 months after the last injection. They will not attend any further study visits (except the unscheduled visit and/or the next schedule visit planned to sign the ICF) and will no longer provide blood samples.

Dengue exposed subjects who consent to continue in the study but decided against receiving the last CYD dengue vaccine injection will be contacted by phone call for a safety follow-up 6 months after the last injection. They will not attend any further study visits (except the unscheduled visit and/or the next scheduled visit planned to sign the ICF) and will no longer provide blood samples.

For dengue exposed subjects who consent to continue in the study and to receive the next CYD dengue vaccine injection, procedures will be as followed:

Vaccinations

Subjects will receive 5 injections, 3 doses of CYD dengue vaccine and 2 doses of Cervarix administered either concomitantly (Group 1) or sequentially (Group 2):

- Group 1: Cervarix and CYD dengue vaccine (concomitantly) at Day (D)0 and Month (M)6, and CYD dengue vaccine (alone) at M12
- Group 2: Cervarix (alone) at D0 and M6, and CYD dengue vaccine (alone) at D0+28D (M1), M6+28D (M7), and M12+28D (M13)

Study Visits

Subjects will have to attend 6 (Group 1) or 8 (Group 2) visits and will have 1 phone call for the 6-month follow-up after the last injection of CYD dengue vaccine. Interim phone calls will be given 7 days (+8 days of time windows) after each injection and approximately 2 months after blood samples during the 6-month period between each vaccination.

An unscheduled visit or phone call will take place during the study pause in order to communicate the new data on the CYD dengue vaccine to each subject (delivering or reading of a “Dear ParticipantLetter”). This visit will be before the next visit initially planned (V07 for most subjects; V08 for 2 subjects). Dengue serostatus at baseline may be communicated to the subjects, if available, at the time of the unscheduled visit.

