**Table 3.1: Study procedures**

Phase IIIb Trial; 5 Injections; **Group 1**: 6 Visits and a 6-month follow-up Phone Call, 4 Blood Samples, 18 Months duration per subject, 6 interim phone calls; **Group 2**: 8 Visits and a 6-month follow-up Phone Call, 6 Blood Samples, 19 Months duration per subject, 8 interim phone calls. Interim phone calls will be given 7 days after each injection (PC1, PC2, PC4, PC5, and PC7) and 2 months after blood samples (PC3, PC6, and PC8) during the 6-month period after each vaccination. As per Protocol Amendment 1, only dengue-immune subjects before the first dengue vaccine injection will be eligible to continue study vaccinations with the CYD dengue vaccine.

Visit (V) Number	Time period prior to Protocol Amendment 1						Time period post Protocol Amendment 1*		
	V01	V02	V03 (Group 2)	V04	V05	V06†‡ (Group 2)	V07†**	V08†	Phone Call§
Trial Timelines	D0	M1 (V01+28D)	M2 (V02+28D)	M6 (V01 + 6M)	M7 (V04+28D) (Group 1) (V02+6M) (Group 2)	M8 (V05+28D)	M12 (V01 + 12M) (Group 1) M13 (V02 + 12M) (Group 2)	M13 (V07+28D) (Group 1) M14 (V07+28D) (Group 2)	M18 (V07+6M) (Group 1) M19 (V07+6M) (Group 2)
Time Windows (days)		+14	+14	±20	+14	+14	±20	+14	+30
Informed Consent and assent form (if applicable) signed	X								
Amendment 1 to AF and ICF						X (Amdt 1) (as applicable)	X (Amdt 1) (as applicable)		
Inclusion/Exclusion Criteria	X								
Significant Medical History	X								
History of Dengue Infection/Vaccination	X								
Demography/Body Stature	X								
Physical/Clinical Examination and Temperature**	X	X (Group 2)	X (Group 2)	X	X	X (Group 2)	X	X	
Concomitant Therapy††	X	X	X (Group 2)	X	X	X (Group 2)	X	X	
Urine Pregnancy Test‡‡	X	X (Group 2)		X	X (Group 2)		X		
Randomization	X			X	X (Group 2)	X	X		
Contraindications		X (Group 2)		X	X (Group 2)	X	X		

Visit (V) Number	Time period prior to Protocol Amendment 1						Time period post Protocol Amendment 1*		
	V01	V02	V03 (Group 2)	V04	V05	V06†‡ (Group 2)	V07†**	V08†	Phone Call§
Trial Timelines	D0	M1 (V01+28D)	M2 (V02+28D)	M6 (V01 + 6M)	M7 (V04+28D) (Group 1) (V02+6M) (Group 2)	M8 (V05+28D)	M12 (V01 + 12M) (Group 1) M13 (V02+ 12M) (Group 2)	M13 (V07+28D) (Group 1) M14 (V07+28D) (Group 2)	M18 (V07+6M) (Group 1) M19 (V07+6M) (Group 2)
Blood Sampling §§ Dengue neutralizing Abs HPV Abs	X (Group 1) X	X X	X (Group 2)		X (Group 1) X	X (Group 2)		X	

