- \*\* A full physical and clinical examination will be performed and documented on each vaccination visit (mandatory before vaccination) and at the Investigator’s discretion if necessary based on the health status of the subject for the other visits.
- †† Concomitant therapy will be collected for Days 0–28 after each injection only
- ‡‡ In healthy female subjects of childbearing potential. Result of urine pregnancy test should be confirmed as negative before vaccination.
- §§ Blood samples planned during vaccination visits will be taken before vaccination
- \*\*\* In such case, 1 unplanned acute blood sample (approximately 3 mL) will be collected for virological confirmation of dengue disease, by NS1 (nonstructural protein 1) antigen test (ELISA), and/or WT dengue RT-PCR
- ††† Interim phone calls will be given 7 days (+8 days of time window) after each injection (PC1: V01 + 7 days, PC2: V02 + 7 days, PC4: V04 + 7 days, PC5: V05 + 7 days, and PC7: V07 + 7 days) and approximately 2 months after blood samples (PC3: M3 or M4, PC6: M9 or M10, and PC8: M15 or M16) during the 6-month period after each vaccination.
- †††† MA will be delivered to subjects who will not receive further CYD dengue vaccine injection but consent to continue their participation in the study.
- §§§§ Solicited injection site reactions will be collected for Days 0–7 after each injection. Solicited systemic reactions will be collected for Days 0–14 after each injection. Unsolicited events will be collected for Days 0–28 after each injection. SAEs will be reported throughout the study and AESIs will be collected in defined time windows according to the type of AESI (hypersensitivity/allergic reactions [serious or not] within 7 days after each CYD dengue vaccine injection, serious viscerotropic disease within 30 days after each CYD dengue vaccine injection, serious neurotropic disease within 30 days after each CYD dengue vaccine injection; serious dengue cases requiring hospitalization [ie, hospitalized suspected dengue case] will be reported during the entire study).
- \*\*\*\* Termination record will be checked either during a planned study visit or a phone call

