##### ***Safety***

All analyses will be descriptive; no hypotheses will be tested. Safety will be assessed for all subjects and for immune subjects after each and any dose of Cervarix and CYD Dengue vaccine. Moreover, a complementary analysis will be performed for each dose of CYD dengue vaccine, for each and any group, on non-immune subjects.

As there are differences in the intensity considered for measurable reactions depending on ages of subjects, a complementary analysis will be performed according to the following age groups: 9-11 years and 12 to 14 years.

For the main parameters, 95% CIs of point estimates will be calculated using the normal approximation for quantitative data and the exact binomial distribution (Clopper-Pearson method, quoted by Newcombe) for single proportions.

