### **5.5 Determination of Sample Size and Power Calculation**

A total of 480 subjects will be enrolled: 240 subjects in each group.

The reference standard deviations (SD) considered for Cervarix are 0.4 for both HPV-16 and HPV-18.

The reference seroconversion rates for Cervarix were set to 99% for both antigens.

The reference SD considered are the following for CYD dengue vaccine: 0.9 for serotype 1, 0.7 for serotypes 2 and 3 and 0.5 for serotype 4 (based on CYD13 and CYD15 efficacy studies conducted in subjects aged 9 to 16 years in Latin American countries).

Considering a potential attrition rate of 15%, such sample size would provide 204 evaluable subjects in the per protocol (PP) population per group. This will give, for the co-primary objectives, a global power of 90.2% and for secondary objectives (in terms of Cervarix seroconversion) a power of 91.8%.

Following Protocol Amendment 1, the number of evaluable subjects may be difficult to achieve (considering only dengue immune (seropositive) subjects at baseline to be included in the Per-Protocol populations). Thus the non-inferiority testing will be done only if the number of evaluable subjects provides a global power of at least 80% for the co-primary objectives and secondary objective ie, if the number of evaluable subjects is at least 163 per group for the co-primary objectives and 168 per group for the secondary objective. The power for non-inferiority in terms of GMTs per antigen and serotype is detailed in Table 5.1 and Table 5.3.

This initial study sample size will also provide a 95% probability of observing an AE that has a true incidence of 1.2% in each group (regardless of baseline serostatus).

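### Any-injection percentages for unsolicited AEs and 28-day SAEs rest on 3 collection windows in the concomitant group and 5 in the sequential group, which flatters co-administration

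*SAP*

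**What the plan says.** **Schedule.** Protocol 5.1.3 describes the concomitant arm as "Group 1: Cervarix and CYD dengue vaccine (concomitantly) at Day (D)0 and Month (M)6, and CYD dengue vaccine (alone) at M12". The sequential arm has every vaccine on its own occasion: Cervarix at the start and at month 6, with the CYD doses following at months 1, 7 and 13. Both arms receive 2 Cervarix and 3 CYD doses, at 3 visits in Group 1 (V01, V04, V07) and 5 in Group 2 (V01, V02, V04, V05, V07).

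**Collection.** A footnote to SAP Table 3.1 states: "Unsolicited events will be collected for Days 0–28 after each injection". SAP 4.4.1.2.3 restricts the unsolicited analysis to onset on days 0 to 28 (or missing). Under Protocol 5.1.4, at Visits 2 and 5, Group 1 gets a diary card for SAEs only, while Group 2 is vaccinated again and starts a full new collection period.

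**Summary.** SAP 5.1.2.2 (Safety) plans results for all subjects and "for immune subjects after each and any dose of Cervarix and CYD Dengue vaccine". SAP 5.2.3 assigns subjects in the pooled summary "and after any dose according to the vaccine received at first dose", and the note in Protocol 12.2.3 ties this to a protocol group. SAP Table 5.1 gives the number and percentage of subjects with a 95% CI, and the number of events. SAP 4.4.1.3.2 reports SAEs both within 28 days of any injection and over the whole study. Neither document uses time at risk or cautions about unequal windows.

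**The concern.** A pooled any-injection percentage counts subjects with at least one event across all their windows, so more windows mean more subjects counted, whatever the vaccines do. A minor illness in the month after V02 or V05 enters the Group 2 unsolicited table. The same illness in Group 1 falls outside any window. For SAEs the imbalance is confined to the 28-day row, because SAEs themselves are collected throughout in both groups.

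Protocol 1.4 gives as a main purpose showing that the two vaccines can be given together safely. Readers will set the two columns of the any-injection table side by side for that purpose, and the ascertainment difference favours the concomitant arm.

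**Working it through.** **Plan's own figures first.** The only safety figure stated is a 95% chance of seeing an AE of true incidence 1.2% in a group. With 240 per group, 1 − (1 − 0.012)^240 = 94.5%, which agrees. The stated interim calls, "6 Visits and a 6-month follow-up Phone Call, 4 Blood Samples, 18 Months duration per subject, 6 interim phone calls" for Group 1 and "8 Visits and a 6-month follow-up Phone Call, 6 Blood Samples, 19 Months duration per subject, 8 interim phone calls" for Group 2, confirm the visit counts. There is one call per vaccination visit plus three after blood samples: 3 + 3 = 6 and 5 + 3 = 8.

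**Collection time.** Days 0–28 are 29 days. Group 1: 3 × 29 = 87 days. Group 2: 5 × 29 = 145 days. The Group 2 total is approximate, because V02 on exactly day 28 shares that day with the V01 window, and likewise V05 with V04.

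**Any-injection percentage at equal per-window risk.** The risk p and the within-subject correlation ρ are assumptions.

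- Independent windows: P(at least one in k) = 1 − (1 − p)^k.
- Correlated windows (beta-binomial): set a = p(1 − ρ)/ρ and b = (1 − p)(1 − ρ)/ρ. Then P(none in k) is the product over j = 0 to k − 1 of (b + j)/(a + b + j).

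Example with p = 10%, ρ = 0.5, so a = 0.1 and b = 0.9:

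- k = 3: 1 − 0.9 × (1.9/2) × (2.9/3) = 1 − 0.8265 = 17.35%
- k = 5: 1 − 0.8265 × (3.9/4) × (4.9/5) = 21.03%

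| p | ρ | Group 1, 3 windows | Group 2, 5 windows | Gap (points) |
|---|---|---|---|---|
| 2% | 0 | 5.9% | 9.6% | 3.7 |
| 10% | 0 | 27.1% | 41.0% | 13.9 |
| 10% | 0.1 | 24.8% | 35.3% | 10.5 |
| 10% | 0.3 | 20.8% | 27.1% | 6.3 |
| 10% | 0.5 | 17.4% | 21.0% | 3.7 |
| 20% | 0 | 48.8% | 67.2% | 18.4 |
| 20% | 0.5 | 32.8% | 38.7% | 5.9 |

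Correlation shrinks the gap but does not reverse it.

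**Where the artefact stops.** Suppose instead that all risk is vaccine-caused, at 10% per injection, and adds independently. Both groups receive 5 injections, so both show 1 − 0.9^5 = 41.0% and the gap is zero. With 10% background per window on top, the figures are 1 − 0.9^8 = 57.0% and 1 − 0.9^10 = 65.1%. The background part alone drives the gap.

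**What a time denominator does.**

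- Background risk of 10% per window: 3 × 0.10/87 and 5 × 0.10/145 both equal 0.345 per 100 subject-days.
- Vaccine-caused risk of 10% per injection: 5 × 0.10/87 = 0.575 against 5 × 0.10/145 = 0.345 per 100 subject-days, a ratio of 1.67 against Group 1.

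Each summary is fair to one kind of event, so both are needed.

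**The case against.** **No comparison is planned.** Safety is described by group and no hypothesis is tested. That stands, and this is a matter of interpretation rather than a flaw in a test. It does not remove the unequal ascertainment from a table that presents both schedules.

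**The pooled reading is not certain.** SAP 5.1.2.2 could mean any dose of each vaccine separately, giving 2 vs 2 and 3 vs 3 windows. Assignment by first dose in SAP 5.2.3 and the note in Protocol 12.2.3 favour pooling, but no table shells are available to settle it. The SAP should say which is meant.

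**Solicited reactions.** A reader might infer that the 7- and 14-day tables are biased in the same way. The documents do not support this in general. Doses are matched over the schedule, and two of Group 1's three windows follow two vaccines, so equal risk per window is not the natural null. For injection-site reactions in particular, both arms have five injection sites.

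**Non-immune subjects.** A reader might also infer that these subjects, who stop before the third CYD dose, will look better than immune subjects because they have 2 vs 4 windows. SAP 5.1.2.2 plans only an analysis by each CYD dose for them. SAP 5.2.3 and 5.2.5 call for presentation by dengue status without specifying an any-dose table.

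**Other rows.** The after-each-dose tables are not all mismatched: at V07 both arms receive CYD alone. Whole-study SAEs and hospitalized dengue do not depend on the windows.

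**Conclusion.** The point holds for unsolicited AEs and for SAEs within 28 days, in the pooled any-injection summary. With equal background risk, Group 2 shows the higher percentage by construction. The gap is 3.7 points at p=2% and 18.4 points at p=20% with independent windows; at p=10% it runs from 13.9 points down to 3.7 as within-subject correlation rises from 0 to 0.5.

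These sizes rest on assumed risks, because the documents give none, and on subjects receiving all doses. A reader might be drawn to a fixed double-digit gap, but that would need both independence and p of about 10% or more, neither of which the documents establish. The direction depends only on the window counts and on some background risk being present. This is a cheap improvement to descriptive output and does not touch the non-inferiority analyses.

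**What to change.** In SAP 5.1.2.2 (Safety):

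1. State that any injection pools all of a subject's doses under her group.
2. Alongside the percentages, report unsolicited AEs and 28-day SAEs per subject-day of open Day 0–28 collection, by group. Count only windows actually opened and count overlapping days once.
3. Footnote the any-injection tables with the window counts: 3 vs 5, and 2 vs 4 for subjects without the third CYD dose if such a table is produced. Say that these percentages are not to be used to compare the schedules.

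Pairing doses instead (Group 1 after V01 against Group 2 after V01 or V02) would not solve this. It still sets one window against two: at p=20% with independent windows, 20.0% vs 1 − 0.8² = 36.0%.

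The cost is a few tables from data already collected. The downside is that the per-day rate weighs against Group 1 for vaccine-caused events, since it has more injections per collection day. The two summaries should be read together.
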